We will carry out a randomized, experimenter- and participant-blinded trial comparing home-based active tDCS and home-based sham tDCS. Participants will be randomized 1:1 to either treatment condition. Half of the participants (n=20) will receive active (constant current intensity of 2mA), while half (n=20) will receive sham tDCS. No changes to the patient's standard care medication will be made. Participants will continue to receive standard treatment for their individual health problems. **Anode and cathode electrodes will be placed over the left and right dorsolateral prefrontal cortices, respectively, with the use of the Omni-Lateral-Electrode system.** Caregivers will set up and administer tDCS for participants with ADRD at home. tDCS will be applied for 30 min at an intensity of 2mA, with 30 s ramping up and down. The same procedure will be used for sham stimulation, but in this case, electric current will be applied only in the first 30s tDCS. All patients, caregivers and clinicians will be blinded to the type of stimulation delivered. We will use bi-hemispheric stimulation (anode F3/cathode F4) based on the facts that bilateral frontal circuits have been implicated in apathy, and bilateral stimulation may have wider effects on brain networks (18, 23, 26). The stimulation will last 30 min according to previous studies (17, 23, 27). According to our previous home-based tDCS protocols (28, 29), all sessions will be remotely supervised by trained research staff (RA), therefore, the sessions will run from Monday to Friday. The remote supervision of the sessions will be possible through video conferencing software (e.g., WebEx), and will ensure the use of proper technique and compliance to the study schedule, also monitoring any adverse events (Fig.1). The devices (tDCS & sham tDCS) will be programmed and cannot be tampered. Participants will be assessed at baseline,

[figure not shown]
[figure not shown]

Fig. 1 Illustrative image of home-based tDCS.

treatment day 14, treatment day 28, treatment day 42, and 6 weeks post-treatment (Fig. 2). The device will be returned in person at the end of the treatment (week 6).

Fig. 2 Proposed outline of the study.

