Acceptability will be evaluated using the method proposed by Ahn et al. (2019) (29). Participants and/or their caretakers will be asked to apply a Likert scale (from 0 [strongly disagree] to 10 [strongly agree]) to answer ten affirmatives regarding the use of home-based tDCS. For example, question 1: "It was easy to prepare the device and accessories", question 7: "I felt confident using the device." Overall acceptability across groups will be evaluated by descriptive measures of satisfaction ratings. GLM will model participant satisfaction ratings as a function of treatment group (active vs. sham tDCS). We expect that participant satisfaction ratings at the end of treatment will demonstrate high acceptance of tDCS treatment in the present sample.

Safety will be assessed with a questionnaire about side effects that include itching, burning, headache, fatigue, and dizziness (29). Descriptive statistics will describe raw frequencies of AEs and side effects. Treatment group differences in AEs and side effects will be evaluated via Chi-square and Fisher's exact test of contingency tables. We expect that adverse events and side effects will be rare, and any that may occur will be mild.

The primary clinical outcome measure will be change on the Apathy Evaluation Scale score (42), the best-validated scale for measuring apathy in AD, which consists of 18 items phrased as questions that are to be answered by the caregiver on a four-point Likert scale, with higher scores indicating greater severity of apathy. Apathy will be

assessed at baseline, during treatment (weeks 2, 4 and 6) and 6 weeks post-treatment. Our hypothesis is that active tDCS group will demonstrate lower apathy scores at the end of treatment relative to sham tDCS. GLM will evaluate residual change by modeling apathy at the end of treatment as a function of treatment group, controlling for apathy at the beginning of treatment. This analysis is a regression-based analogue to ANCOVA that permits non-normally distributed outcome distributions. Follow-up analyses will evaluate change over time across groups via GLM with multilevel components (GLMM) as well as cross-sectional analyses within each measurement time point via GLM.

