The secondary clinical outcome measures will include: (1) total score on the Brief Dimensional Apathy Scale (bDAS) (43); (2) total score on the NPI-Q which evaluates 12 discrete NPS considering their severity and the related caregiver distress (38-40); (3) depressive symptoms as assessed by the Cornell Scale for Depression in Dementia (41); (4) cognition as evaluated by the Mini-Mental State Examination (MMSE), which includes memory, language, praxis and orientation tasks, yielding a global cognition score ranging 0 to 30, with higher scores indicating better performance (35).

Our hypothesis is that active tDCS group will demonstrate lower scores on the bDAS, NPI-Q and Cornell Scale for Depression, and higher scores on the MMSE at the end of treatment relative to sham tDCS. GLM will evaluate residual change in each outcome (in separate models) by modeling scores at the end of treatment as a function of treatment group, controlling for baseline.

Sociodemographic data (gender, age, marital status and education) will be collected at the baseline. Clinical (health history, use of medication and life habits) and anthropometric data will be collected at the baseline and after the treatment period. These data will be control variables for the study.

Table 1. Timetable for Collection of Data

Assessment	Baseline	Week 2	Week 4	Week 6	Week 12
Medical History Questionnaire	X				
MMSE	X			X	X
AES (primary outcome)	X	X	X	X	X
NPI-Q	X	X	X	X	X
bDAS	X	X	X	X	X
Cornell Scale for Depression	X			X	X
tDCS experience questionnaire		X	X	X	X
Side effects questionnaire		X	X	X	X

Data and Safety Monitoring

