Inferential Paradigm and Bayesian Analyses. Following recommendations in the clinical trial literature analyses we will proceed using parallel frequentist and Bayesian statistical inference (30, 31). The Bayesian inferential paradigm can provide probabilistic estimates of effects irrespective of sample size. Bayesian analyses will focus on posterior probabilities ≥ 0.75 (equivalent to a Bayes factor = 0.33 or 3.0) that parameter estimates are greater or less than zero to emphasize the value in discerning treatment effects in a small trial. Power calculations for the frequentist analyses are derived using G*Power v. 3.1.9.2 and focus on the residual change model described in Hypothesis 2a. As noted, the Bayesian analyses will provide the primary inferential results; sample size considerations for the frequentist analyses are limited by the small sample size and provided as due diligence. Given alpha = 0.05, a sample size N = 40 provides 80% power to detect a Cohen's $f = 0.45$. Frequentist analyses will provide conventional interpretation of the relationships between predictors and outcomes: the probability of the data, given the null hypothesis. Bayesian analyses will incrementally update specified prior information regarding effects to directly yield the probability of an alternative hypothesis. Bayesian analyses will employ informative priors as they develop in the literature; otherwise, weakly informative priors will be used as a default (e.g., for regression coefficients: $\sim N[\mu=0, \sigma^2=100]$; for non-linear outcome variables this prior applies to the coefficient within the link-function). Sensitivity analyses using optimistic and pessimistic, skeptical priors will evaluate prior assumptions. Assessing the convergence of Bayesian analyses on the posterior distributions via Monte-Carlo Markov chain (MCMC) will use diagnostic evidence including effective sample size and scale reduction factors.

Evaluation of posterior distributions will permit statements regarding the probability that effects of varying magnitudes exist, given the data, even with a small sample size.

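### Safety is a primary objective, but its planned analysis (raw frequencies and group tests at 20 per arm) includes no measure of precision

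*Combined protocol and SAP*

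**What the plan says.** The Objectives table places safety in the primary objective, beside feasibility and acceptability. The safety paragraph of Study Procedures gives its analysis in two sentences: "Descriptive statistics will describe raw frequencies of AEs and side effects", and "Treatment group differences in AEs and side effects will be evaluated via Chi-square and Fisher's exact test of contingency tables". An expectation follows: "We expect that adverse events and side effects will be rare, and any that may occur will be mild". No rate is attached to the word rare.

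Study Design fixes the arm sizes: "Half of the participants (n=20) will receive active (constant current intensity of 2mA), while half (n=20) will receive sham tDCS". Table 1 schedules the "Side effects questionnaire" at weeks 2, 4, 6 and 12; stimulation ends at week 6.

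The only power figure is in the Statistics section (repeated under Study Design): "Given alpha = 0.05, a sample size N = 40 provides 80% power to detect a Cohen's" f of 0.45. The power calculations "focus on the residual change model described in Hypothesis 2a", which concerns apathy. The same section makes the Bayesian results primary in general and names logistic and count models for binary and count data, but ties none of this to side effects.

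For safety, the plan does not state an interval, which of the two tests governs, whether chi-square is continuity-corrected, or how four questionnaires per person become one table.

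**The concern.** A small trial with safety as a primary objective should report how high a side-effect rate its data still allow, and how large a difference between arms. Raw frequencies and a p-value do not report either. If the comparison comes out non-significant, as is likely at this size even when a sizeable excess exists, the report would hold no stated figure to stop a reader from taking the result as reassurance. The safety findings are also meant to guide adjustment or expansion of the protocol (Publication Plan), so the uncertainty should be visible in them.

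**Working it through.** **Inputs.** 20 per arm (Study Design); two-sided 0.05 (the plan gives alpha 0.05 without sidedness, so two-sided is assumed); expected completion above 70% (Study Procedures). Side-effect rates are assumptions, because the documents give none.

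**1. The plan's own power figure.** With f = 0.45 and N = 40, the noncentrality is N × f² = 40 × 0.2025 = 8.1. The noncentral F with 1 numerator degree of freedom gives power of 79.2% (38 denominator df) or 79.1% (37 df, one covariate). A normal approximation with d = 2f = 0.9 and 20 per arm gives 81.2%. The stated 80% is reproduced. It applies to apathy and gives no assurance for safety.

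**2. Power of the safety tests.** There are 21 × 21 = 441 possible tables (a events of 20 active, b of 20 sham). Power is the sum of Bin(a; 20, p1) × Bin(b; 20, p2) over all tables with p < 0.05.

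| Assumed true rates, active v sham | Fisher | Chi-square, uncorrected |
|---|---|---|
| 10% v 5% | 2% | 5% |
| 20% v 5% | 17% | 29% |
| 30% v 5% | 45% | 59% |
| 30% v 10% | 24% | 36% |
| 40% v 10% | 49% | 62% |
| 50% v 10% | 74% | 84% |

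With no sham events, Fisher's test needs at least 5/20 active events to reach 0.05 (5 v 0: p = 0.047; 4 v 0: p = 0.106). Nor does a null comparison bear on how common a symptom is: 10/20 v 8/20 gives Fisher p = 0.75 with half the active arm affected.

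**3. What intervals would show.** The exact (Clopper-Pearson) 95% upper limit for zero events in n is 1 - 0.025^(1/n).

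- 0/20: 1 - 0.025^(1/20) = 16.8% (one-sided 95%: 1 - 0.05^(1/20) = 13.9%)
- 1/20: 0.1% to 24.9%
- 2/20: 1.2% to 31.7%
- 0/14, where 14 = 0.70 × 20 if losses are equal: upper limit 23.2%

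For the risk difference at 2/20 v 1/20, the estimate is 10% - 5% = 5 points. The Wilson limits are 2.8% to 30.1% and 0.9% to 23.6%. Newcombe's method gives

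- lower: 5 - √[(10 - 2.8)² + (23.6 - 5)²] ≈ -15 points
- upper: 5 + √[(30.1 - 10)² + (5 - 0.9)²] ≈ +26 points (25.5 unrounded to whole points)

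**4. How often the two named tests conflict.** For 4/20 v 0/20:

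- uncorrected chi-square = 40 × (4×20 - 16×0)² / (20×20×4×36) = 4.44, p = 0.035
- with continuity correction = 40 × (80 - 20)² / 57,600 = 2.5, p = 0.114
- Fisher, two-sided = 2 × 4,845 / 91,390 = 0.106

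Over all 441 tables, uncorrected chi-square and Fisher fall on opposite sides of 0.05 in 28, always with chi-square significant and Fisher not. With the correction they differ in 8. The probability of a conflict (uncorrected) is 1.0% to 2.8% at equal rates of 5% to 30%, 12.4% at 20% v 5% and 14.5% at 30% v 5%.

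**The case against.** The fair defence is that this is a 40-person feasibility trial sized by recruitment and funding (Study Population). It claims no power for safety, and low power at 20 per arm cannot be cured by wording. Frequencies are planned separately from the tests, and once participant counts are published any reader can derive the 16.8% limit for 0/20. All of that stands. It does not remove the point: where tests are weak, intervals are the informative summary, and the authors' conclusion should rest on them. The general Bayesian text could in principle supply intervals, but no safety model is named.

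A reader might also infer four stronger things, which the documents do not support.

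- **That rarity will be inferred from a null test.** The sentence on rarity is an expectation, like those for consent, completion and satisfaction. Nothing links it to the group comparison.
- **That the two tests contradict each other as a rule.** They can, but seldom do, and the 4/20 v 0/20 conflict disappears if chi-square is continuity-corrected.
- **That chi-square is unreliable here and Fisher alone must be used.** Over equal rates of 5% to 50%, the actual type I error of uncorrected chi-square is 1.2% to 5.3%; Fisher's is 0.2% to 2.5%. Requiring Fisher would cut power from 59% to 45% at 30% v 5%, a real cost when looking for harm.
- **That participants will be counted more than once, or week 12 pooled with treatment.** The unit and window are not stated, and pooling is not planned anywhere. This is missing detail, not an error.

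**Conclusion.** The point holds as one about precision. A primary objective is analysed by frequencies and by tests that would miss a 20% v 5% difference 83% of the time with Fisher (100 - 17) or 71% with uncorrected chi-square (100 - 29), and no interval is planned. The power figures rest on assumed event rates, two-sided testing and all 40 participants contributing; fewer completers would make matters worse. The 16.8% limit needs no assumed rate, only 20 assessed participants in the arm. The missing rule for choosing a test is a lesser matter, and the trial's conduct is not in question. The change is worth making before the data are unblinded, because it improves what the trial can conclude at almost no cost.

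**What to change.** In the safety paragraph and the Statistics section:

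1. For each symptom, report the number of participants per arm with any occurrence during the treatment period (questionnaires at weeks 2, 4 and 6), with the denominator. Show week 12 separately.
2. Give an exact 95% interval for each arm's proportion and a 95% interval (for example Newcombe's) for the risk difference.
3. Base the safety conclusion on those intervals, with the group test as supportive only.
4. State in advance which test governs and, if chi-square, whether it is continuity-corrected. Either test is defensible: Fisher is the more conservative, uncorrected chi-square the more powerful.

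This needs SAP wording and a few extra table columns, with no new data and no change to assessments. The downside is a more cautious safety statement: even a symptom never reported in an arm of 20 would be described as compatible with rates up to 16.8%.

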Given the clinical relevance of apathy in ADRD, the equivocal results of the therapeutic resources available to address it, and the emerging evidence of safety and efficacy of tDCS in ADRD, our proposal aims to test the feasibility, safety and efficacy of home-based tDCS for the treatment of apathy in ADRD. Home-based tDCS circumvents critical problems observed in previous trials (25), including the need of multiple visits to medical centers for tDCS application, allowing a more intensive application (e.g. 5 x per week) for prolonged periods.

Objectives

Objectives	Outcome Measures

Primary objective To assess feasibility, acceptability, and safety of providing tDCS to ADRD patients with apathy.
	
Feasibility measures will include recruitment rate (per month), randomization success, blind success, retention, and attrition rates.
 
Acceptability will be evaluated using Likert scale (from 0 [strongly disagree] to 10

	[strongly agree]) to answer ten affirmatives regarding the use of home-based tDCS. Safety will be assessed with a questionnaire about side effects that include itching, burning, headache, fatigue, and dizziness.
Secondary objectives To assess the efficacy of tDCS for ADRD-related symptoms, with a primary focus on apathy.	Neuropsychiatric symptoms and cognitive measures evaluated through validated tools.

Study Design

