Descriptive statistics will evaluate measures of central tendency and frequencies for all continuous and categorical variables (respectively) measured in the study. Correlation analyses (i.e., Pearson's r , Spearman's ρ) will be used to evaluate broad patterns of relationships across variables. Preliminary data analyses will inspect relationships between sample characteristics (e.g., demographics), experimental group (e.g., active vs. sham tDCS), and specified outcome variables (e.g., Apathy) via traditional statistical tests (e.g., chi-square; Mann-Whitney; t -tests). Any sample characteristic variables that demonstrate a relationship with both predictor and outcome variables in a given model meet criteria for being a potential confounder (32, 33) and will be included as a covariate in such models for hypothesis testing.

Statistical modeling will primarily use generalized linear modeling (GLM) with multilevel components (GLMM) for correlated observations. Potentially nonlinear relationships between predictors and outcomes will be evaluated via inclusion of polynomial or spline effects. Continuous, dichotomous, and count-distributed data will utilize linear, logistic, and Poisson/negative binomial regression, respectively (each with a canonical link function). Evaluation of distributional assumptions will use residual plots, formal statistical tests, and posterior predictive checking. Violations of assumptions will be addressed via transformation, robust estimation, stratification, and/or coefficient scaling where appropriate. Statistical analyses will be performed using the R statistical computing environment via packages lme, rstan, and brms.

Missing data will be addressed via maximum likelihood, explicit modeling of missingness, or imputation where appropriate. Each approach is robust to ignorable missingness (i.e. MCAR and MAR). Sensitivity analyses will permit evaluation of the robustness of findings to missing data assumptions. While Bayesian analyses are not influenced by traditional concerns of multiplicity, for the frequentist analyses, all primary outcome variables (those specified by name in the hypothesis statements) will be evaluated at the $\alpha = 0.05$ statistical significance level, while any secondary or otherwise post hoc analyses will employ false discovery rate (FDR) to control for Type I error.

Ethics/Protection of Patient Confidentiality

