Potential Benefits to Research Participants. If our hypothesis is correct, subjects in the active arm of the study might benefit from the study participation. Importantly, the results will be relevant to the field of AD and neuromodulation.

Significance

Our proposal will address a frequent and sometimes overlooked clinical problem in patients with ADRD, i.e. apathy. The proposal can advance the field of non-pharmacological strategies for NPS, also presenting a great potential for clinical translation. Home-based intervention with real-time monitoring through a secure conferencing platform is a new modality for improving symptom management in ADRD. Moreover, home-based, remotely supervised tDCS has advantages over clinic-based sessions, considering the time and cost associated with attending multiple sessions over several days. Caregivers will be trained at the in-person baseline visit, and all the tDCS sessions will be remotely supervised via secure videoconferencing software by trained research staff for the entire duration of each session to ensure the use of proper technique and to monitor any adverse events.

Costs and Compensations

Subjects will not be charged for tests, procedures or other costs incurred solely for the purposes of this research. Patients will receive a voucher of US 50.00 for their time dedicated to each evaluation (total number of assessments = 5).

This project was approved to receive financial support from Texas Alzheimer's Research and Care Consortium (TARCC) 2020 Grant Program.

Publication Plan

This study will represent an original contribution to the areas of non-pharmacological approaches for NPS in ADRD and neuromodulation in ADRD, also fostering home-based interventions. More importantly, we expect to have enough evidence on the feasibility, acceptability, safety and efficacy of tDCS for apathy in AD so we can adjust and/or expand the protocol, ultimately, aiming its translation into the clinical practice. This project, if granted, will also strength emerging clinical research groups at UTHealth working with novel technologies that can be applied to ADRD and other neuropsychiatric conditions.

References

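### Safety is a primary goal, but the arms are compared only by a chi-square/Fisher test at 20 per arm, with no risk difference, confidence interval or upper bound

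*Combined protocol and SAP*

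**What the plan says.** The Objectives table gives the primary objective as "To assess feasibility, acceptability, and safety of providing tDCS to ADRD patients with apathy". The safety analysis is in the safety paragraph of Study Procedures and has three parts:

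- a description: "Descriptive statistics will describe raw frequencies of AEs and side effects";
- a comparison: "Treatment group differences in AEs and side effects will be evaluated via Chi-square and Fisher's exact test of contingency tables";
- an expectation: "We expect that adverse events and side effects will be rare, and any that may occur will be mild".

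The Study Design section fixes the arm sizes: "Half of the participants (n=20) will receive active (constant current intensity of 2mA), while half (n=20) will receive sham tDCS". The Publication Plan states "we expect to have enough evidence on the feasibility, acceptability, safety and efficacy of tDCS for apathy in AD", and this is to serve as the basis for adapting or enlarging the protocol.

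The Statistics section (repeated under Study Design) makes Bayesian inference primary, names logistic and count regression for data of those types, and gives one power figure, for the apathy model. It names no safety model, prior or threshold. The sample size rests on recruitment and funding (Study Population).

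**The concern.** A test of no difference answers whether the data are surprising if the arms are equal. A safety goal asks how common side effects are under active stimulation and how large an excess over sham is still compatible with the data. The plan names no quantity that answers either question. Feasibility, in the same objective, at least has numerical expectations (more than 80% consenting and more than 70% completing); safety has only the words rare and mild.

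The weakness is greatest where the plan expects to be. When events are few, the test is likely to be non-significant if there is no excess and also likely to be non-significant if there is a large one. The trial is meant to inform wider use of home stimulation in people with dementia, and a p-value of that kind would tell the next team little about harm.

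**Working it through.** **Inputs from the documents.** 20 participants per arm (Study Design). Level 0.05: outcomes named in the hypotheses "will be evaluated at the $\alpha = 0.05$ statistical significance level" (Statistics). Sidedness is not stated; I take two-sided. No multiplicity adjustment is applied, although "any secondary or otherwise post hoc analyses will employ false discovery rate (FDR) to control for Type I error", and using it across the separate side effects would lower power further.

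**Assumptions.** The documents give no side-effect rate. I read rare as a sham rate of about 5% to 10% and show higher and lower rates as well. Each participant counts once, yes or no. The questionnaire is given at weeks 2, 4, 6 and 12 (Table 1), and the plan does not say whether events are counted per participant, per visit or per symptom.

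**Step 1: the plan's own power figure.** It states 80% power at Cohen's f = 0.45 and N = 40 for the apathy model. With noncentrality N × f² = 40 × 0.45² = 8.1 and an F test on 1 and 37 degrees of freedom (one covariate), power is 79.1%, which agrees to within rounding. It says nothing about safety.

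**Step 2: chance of missing a tripling.** With p0 the sham rate and p1 = 3 × p0 the active rate,

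miss rate = 1 − Σ Bin(x; 20, p1) × Bin(y; 20, p0), summed over all tables (x, y) with p ≤ 0.05.

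All 21 × 21 tables were enumerated.

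| Sham → active | Fisher misses | Chi-square (uncorrected) misses |
|---|---|---|
| 2% → 6% | 99.6% | 98.0% |
| 5% → 15% | 93% | 85% |
| 10% → 30% | 76% | 64% |
| 15% → 45% | 56% | 43% |
| 20% → 60% | 35% | 25% |
| 25% → 75% | 17% | 10% |

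The miss rate is two thirds or more only while the sham rate is at most about 12.5% (Fisher) or 9.4% (chi-square).

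**Step 3: what significance requires.** With no sham events, Fisher's test needs at least 5 active events and chi-square 4. With one sham event they need 7 and 6.

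**Step 4: what an interval would add.**

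- 3/20 active against 1/20 sham: Fisher p = 0.60. The risk difference is 15% − 5% = +10 points, with a 95% Newcombe interval of −11 to +31.
- 7/20 against 2/20: Fisher p = 0.127, chi-square p = 0.058. The risk difference is 35% − 10% = +25 points, with an interval of −1 to +48.
- 0/20 active: exact upper limit 1 − 0.025^(1/20) = 16.8% (two-sided 95%), or 1 − 0.05^(1/20) = 13.9% (one-sided 95%).
- 1/20 and 2/20 active: two-sided upper limits 24.9% and 31.7%.

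In the first two cases the p-value alone reports no significant difference, while the interval shows that a large excess has not been excluded.

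**The case against.** Five points can be made for the plan.

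- **Low power for uncommon harms is normal in a 40-person feasibility trial.** This stands. The sample size is not the defect; the defect is that the analysis does not report what 20 per arm can and cannot exclude.
- **The miss rate depends on the sham rate.** This stands. Sham delivers current for the first 30 seconds of each session and the questionnaire is repeated four times, so a cumulative sham rate above 10% for itching or burning cannot be ruled out. A reader might infer that a tripling is missed two times in three whatever the rate, or that the test hardly ever rejects. Neither follows: at 10% against 40% the miss rates are 51% (Fisher) and 38% (chi-square), so the tests reject 49% and 62% of the time.
- **The plan never equates non-significance with safety.** This stands. Its expectation is absolute, and raw frequencies are reported beside the test. In the 7/20 example, 35% of the active arm would visibly contradict rare whatever the p-value. But the plan gives no other rule for judging active against sham.
- **The Bayesian framework could supply magnitude statements.** This stands only as a general possibility. Study Procedures assigns regression models to acceptability and apathy but contingency-table tests to safety.
- **Readers can compute intervals from the frequencies.** They can, but a conclusion on a primary objective should rest on a quantity named beforehand.

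A reader might also recompute power at 14 per arm from the 70% completion figure. That is a floor for study completion. Side effects are recorded from week 2 and sessions are supervised, so non-completers can contribute safety data.

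**Conclusion.** The point holds in this form: for a primary goal, the only named between-arm safety analysis is a test of difference, with no effect estimate, interval or bound. At assumed sham rates of 5% to 10%, a tripling is missed between 64% and 93% of the time, depending on the rate and the test. At 15% the figures are 56% / 43%, and at 20% they are 35% / 25% (Fisher / chi-square). These results rest on 20 evaluable participants per arm, one yes/no outcome each, a two-sided 0.05 level and no multiplicity adjustment.

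A reader might go further and say that the plan will declare the device safe on a non-significant p-value. The documents state no such rule. What they support is narrower: at the event rates the plan expects, this test cannot separate no excess from a material excess, so it cannot carry the safety conclusion. The change should be made, because it alters what the trial can say about safety and costs little.

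**What to change.** Amend the safety paragraph of Study Procedures as follows.

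1. Count each event once per participant, among all randomised participants who received at least one session.
2. For any adverse event, any serious adverse event and each named side effect, report the active-arm proportion with an exact 95% confidence interval, and the active-minus-sham risk difference with a 95% interval (Newcombe or exact).
3. Base the safety statement on these estimates and their upper limits. Keep Fisher's test as descriptive only.
4. Add a sentence such as: a non-significant difference will not be taken as evidence of safety; with 20 participants in the active arm, zero events excludes only true rates above about 17% (two-sided 95%).

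This does not set a tolerable excess. That is a clinical judgement, and if the sponsor has one in mind it should be stated before the data are seen.

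The cost is a few sentences and some table columns, with no new data or patients. The intervals will be wide, and the safety statement will read less favourably than a non-significant p-value would.

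### The plan expects side effects to be mild, but its safety analysis specifies no severity grade or severity summary, so it can address how often they occur and not how bad they are

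*Combined protocol and SAP*

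**What the plan says.** Safety is one of the three components of the primary objective (General Information; Objectives). Study Procedures measures it with a questionnaire that names five symptoms: itching, burning, headache, fatigue and dizziness. The questionnaire is otherwise described only by a citation, and its response format is not given. Table 1 schedules it at weeks 2, 4, 6 and 12.

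The planned summary is: "Descriptive statistics will describe raw frequencies of AEs and side effects". The planned comparison is: "Treatment group differences in AEs and side effects will be evaluated via Chi-square and Fisher's exact test of contingency tables". The rows and columns of those tables are not defined. The stated expectation is: "We expect that adverse events and side effects will be rare, and any that may occur will be mild". Neither rare nor mild is given a definition or threshold.

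On exposure, Study Design says of the active arm: "tDCS will be applied for 30 min at an intensity of 2mA, with 30 s ramping up and down". Of the control arm it says: "The same procedure will be used for sham stimulation, but in this case, electric current will be applied only in the first 30s tDCS". The arms have 20 participants each.

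Nothing elsewhere fills the gap. The Statistics section has general modelling, multiplicity and missing-data rules but nothing on severity. Data and Safety Monitoring deals with data storage and sharing. Protection Against Potential Risks calls side effects uncommon and mild, but as background rather than as something the trial will measure.

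**The concern.** A frequency can answer whether side effects were rare. It cannot answer whether those that occurred were mild. Half of the stated expectation for a primary objective therefore has no planned evaluation. Other outcomes do have a stated scale: acceptability is rated 0 to 10, and the NPI-Q takes severity and caregiver distress into account.

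The sham procedure adds to this. Both arms receive current at the start of each session, so itching or burning at onset can be reported in either arm. The active arm then continues for 30 minutes. If symptoms there are stronger or more persistent, a table of occurrence would not show it.

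The Publication Plan expects the trial to give enough evidence on safety to adjust or expand the protocol, with clinical practice as the final aim. A statement that effects were mild would feed that decision without an analysis behind it, in people with dementia treated at home by caregivers.

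**Working it through.** **1. The plan's own figure.** The only power statement is for apathy: N = 40, alpha 0.05, Cohen's f = 0.45, 80%. With one covariate, the noncentrality is f² × N = 0.2025 × 40 = 8.1 on 1 and 37 degrees of freedom, which gives 79.1%. The figure reproduces, but it says nothing about safety. No side-effect rate is given for either arm, so every rate below is an assumption.

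**2. Expectation against analysis.**

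| Part of the expectation | Planned quantity | Addressed? |
|---|---|---|
| Rare | Raw frequencies; chi-square/Fisher by arm | Yes, though without a threshold |
| Mild | None specified | No |

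**3. Equal occurrence with unequal severity (assumed counts, 20 per arm).**

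| Worst grade | Sham | Active |
|---|---|---|
| None | 10 | 10 |
| Mild | 9 | 2 |
| Moderate | 1 | 6 |
| Severe | 0 | 2 |

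Any occurrence is 10/20 versus 10/20, two-sided Fisher p = 1.00. Moderate or worse is 1/20 versus 8/20, p = 0.020.

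**4. Power of the two comparisons.** Exact power is the sum, over all pairs (a, b), of Bin(a; 20, p_active) × Bin(b; 20, p_sham), counting the pairs with two-sided Fisher p ≤ 0.05. Three assumed cases with equal occurrence:

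| Any occurrence, both arms | Power, any occurrence | Moderate or worse, sham vs active | Power, moderate or worse |
|---|---|---|---|
| 50% | 2% | 5% vs 40% | 72% |
| 70% | 2% | 10% vs 50% | 74% |
| 20% | 2% | 2% vs 15% | 12% |

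With equal occurrence the first test can only reject by chance, so 2% is its actual size. The last row shows that grading does not rescue a small sample when events are few.

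**5. Occurrence rates that do differ (20 per arm, same formula).**

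| Sham vs active, any occurrence | Fisher power |
|---|---|
| 5% vs 15% | 7% |
| 5% vs 30% | 45% |
| 10% vs 30% | 24% |
| 30% vs 50% | 16% |
| 50% vs 80% | 41% |

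A non-significant result is the likely outcome in every row although a real difference exists. Power is lowest in the first row, where sham events are rare, so the sample size alone is enough to make the comparison weak.

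**6. What a graded table would report.** Exact two-sided 95% intervals for moderate-or-severe at 20 per arm: 0/20 gives 0 to 16.8% (upper limit 1 − 0.025^(1/20)), 1/20 gives 0.1% to 24.9%, and 8/20 gives 19.1% to 63.9%. These are wide, but they describe the quantity that the expectation is about.

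**The case against.** The strongest reply is that the documents do not show severity to be unrecorded. The questionnaire is cited rather than described and may carry a grade. The contingency tables have no defined rows, so an arm-by-grade table would fit the wording. The expectation is not a decision rule, and the plan does not say that it will conclude mild from frequencies. Trained staff also supervise every session remotely and monitor adverse events. All of this stands, and it limits the point to the analysis as described. It does not supply the missing severity summary.

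A reader might go further and infer three things that the documents do not support.

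- **That the safety endpoint only counts occurrence.** This is true of the described summary but not established for the instrument, for the reasons just given.
- **That occurrence will approach 100% in both arms.** Six weeks of Monday-to-Friday treatment is 6 × 5 = 30 sessions. With an assumed 2%, 5% or 10% chance of a sensation per session, 1 − (1 − p)^30 gives 45%, 79% or 96% ever affected. But these rates have no source in the documents, and the lowest result is nowhere near a ceiling. The questionnaire is given at four visits, not per session. The formula also assumes independent sessions. With an assumed within-person correlation of 0.3 (beta-binomial), the results are 12.5%, 28.5% and 49.2%.
- **That the sham current is what makes the comparison insensitive.** The onset argument fits itching and burning but is not made for headache, fatigue or dizziness. Occurrence could also differ between arms, since active current lasts 30 minutes. Twenty per arm already gives low power when sham events are rare (step 5).

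**Conclusion.** The point holds in a limited form. As described, the safety analysis can address rare but not mild, because no severity grade, definition of mild or severity summary is specified anywhere. That conclusion rests on the text alone. Because sham also delivers current at onset, similar occurrence percentages would not show similar severity. At 20 per arm, a non-significant occurrence test would not show comparable tolerability in any case: power is 7% to 45% over the assumed differences in step 5. The size of any active-sham difference in severity cannot be estimated from the documents, and the counts and rates in the working are illustrations.

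This is a worthwhile, inexpensive improvement to a component of the primary objective. It does not affect the efficacy analysis.

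**What to change.** In the safety paragraph of Study Procedures:

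- State whether the cited questionnaire grades severity. If it does, use that grade. If not, record each side-effect item and each adverse event as none, mild, moderate or severe on the form already scheduled at weeks 2, 4, 6 and 12.
- Report the worst grade per participant by arm. Include the proportion with any moderate-or-severe effect and its 95% interval, beside the any-grade frequency.
- Define the rows and columns of the contingency tables accordingly.
- Base any statement that effects were mild on this table, and do not read a non-significant test as evidence of comparable tolerability.

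The cost is a slightly longer form and one more table, or wording alone if severity is already graded. The intervals will be wide at 20 per arm, and grading does not change that.
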